9.3 POPULATIONS FOR ANALYSES

Our primary population for analyses will be the intention-to-treat population. For a sensitivity analysis, the per-protocol population will also be considered. The per-protocol dataset includes subjects who complete the three visits and answer 'yes' to watching all booster messages.

9.4 STATISTICAL ANALYSES

9.4.1 GENERAL APPROACH

Randomization

A block-level randomization scheme with a 1:1 allocation ratio will be used to determine interventions for individuals. Random block sizes of 2, 4, and 6 will be used to create the randomization scheme. Randomization will be stratified on primary language and site to ensure balance between the intervention groups. There will be 12 possible sites in the study.

9.4.2 ANALYSIS OF THE PRIMARY ENDPOINT(S)

Primary efficacy

The primary outcome is caries status, measured by the d_1d_{2-3} caries criteria for scoring dental caries in children developed by members of the Iowa Fluoride Study. Caries status as total counts of dmf surfaces will be calculated during yearly dental exams. These counts will be reported as means, medians, quartiles, standard deviations, and ranges for each intervention group. Data will be explored longitudinally using dmf surfaces at each age and dmf increments between ages. Analysis of caries outcomes will focus on Poisson and/or negative binomial modeling, possibly with variance inflation and zero inflation accommodation, as appropriate. To account for repeated longitudinal measurements, generalized estimating equations (GEEs) will be used to model these counts. A first-order autoregressive or AR(1) working correlation structure will be

assumed. The quasi-likelihood information criteria (QIC) will be used to compare models to select the best fit. The model will include age, gender, location (urban/rural), race, intervention, and mothers' knowledge and behavior. These are all clinically important known covariates that are associated with caries status, and mothers' intervention and behavior/knowledge are covariates of interest. These are planned covariates to include; however, if the number of covariates is limited by the sample size or infrequent observations of caries, we will use bivariate analyses to inform a more parsimonious final model. Results for the model will be presented as incidence rate ratios with 95% confidence intervals. Data will be analyzed on an intention-to-treat basis with sensitivity analyses considering the per-protocol dataset. Missing data will be addressed via multiple imputation and sensitivity analyses will be conducted to explore potential impacts on results.

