1 PROTOCOL SUMMARY

1.1 SYNOPSIS

Title: Grant Number:	Birth to Three – Cavity Free: Effectiveness of a Psychoeducational Intervention for ECC Prevention				
Grant Number: Study Description:	UG3DE029443 This study is considered a Stage II research study accord NIH Stage Model ¹ and will implement an evidence-based behavioral intervention to help expectant mothers develo oral health habits early in their future child's life. The cen hypothesis is that a theory-based intervention approach fa by the self-determination theory (SDT) using videotaped and targeted to mothers of high-risk young children will an elevated sense of perceived autonomy, competence, ar relatedness, which will in turn lead mothers to experience demonstrate improved self-reported knowledge and beha concerning their child's oral health. Consequently, their of have more positive oral health outcomes, indicated by low of caries, dental plaque, and mutans streptococci (MS).				
Objectives*:	Primary Objective:	1.	To test the effectiveness of a multi- component behavioral intervention for pregnant mothers on the subsequent oral health status of their children at ages 12, 24, and 36 months.		
	Secondary Objectives:	2b	To test the degree to which the intervention produces its effects on children's oral health status through its mediating effects on mothers' changes in self-reported knowledge. To test the degree to which the intervention produces its effects on children's oral health status through its mediating effects on mothers' changes in behaviors concerning their child's oral health (i.e., oral hygiene habits, dietary habits, use of fluoride, visits to the dentist, lift-the-lip to check for early signs of cavities). To test the degree to which the intervention improves other		
			indicators of oral health status in children (levels of salivary MS and visible dental plaque scores among the children).		

Endpoints:*	Primary Endpoint:	The primary outcome of interest is children's caries status, as measured by the number of decayed, missing or filled surfaces using the d_1d_{2-3} mfs scoring method. Both d_{2-3} and d_1 levels, derived from the d_1d_{2-3} mfs caries criteria, will be considered, reflecting numbers of affected (cavitated, missing due to caries or filled) surfaces with and without inclusion of non-cavitated (d_1 "white spot") lesions.			

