1.3 SCHEDULE OF ACTIVITIES

Study time-points and corresponding activities for ALL	Visit 1 Prenatal				Visit 2 Age 1 to 2			Visit 3 Age 2 to 3			Visit 4 Age 3+		
study participants in the experimental and control groups	Visit 1 at WIC	1-Month Follow-up	3-Month	9-Month Follow-up	Visit 2 at WIC	l -Month Follow-un	3-Month	9-Month Follow-up	Visit 3 at WIC	l -Month Follow-up	3-Month	9-Month Follow-up	Visit 4 at WIC
Informed Consent	\checkmark												
Group randomization	\checkmark												
Mother demographic questionnaire	~												
Mother knowledge questionnaire	~	✓		~	✓	~		~	✓	✓		~	✓
Mother behavior questionnaire	~	✓		~									
Intervention videotaped oral health message	~				~				✓				
Internalization questionnaire	~				~				~				
Health care climate questionnaire (HCCQ)	~				~				~				
Booster videotaped oral health message			~				✓				~		
Child plaque sample					\checkmark				\checkmark				✓
Child dental exam: plaque, caries and tooth status recordings					✓				~				✓
Child behavior questionnaire				~	✓	~		~	✓	~		~	~
Mother & child demographic questionnaire					~				~				✓
Mother behavior intent questionnaire													✓

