- Prior to watching the videotaped messages at visits 1, 2 and 3, participating women from both groups will complete a series of pre-intervention questionnaires regarding their own oral health and their (future) child's oral health. The questionnaires will include information regarding the mother's (1) demographics; (2) perceptions and status of their own oral health; and (3) pre-intervention self-reported knowledge and behavior concerning their own oral health (dietary/oral hygiene behaviors, frequency of visits to the dentist, etc.), as well as concerning their child's oral health (child's dietary/oral hygiene habits, etc.).
- Immediately after viewing the videotaped oral health messages at visits 1, 2 and 3, participating women from both groups will complete two additional questionnaires to assess their perceptions of the degree of autonomy support of the videotaped messages. One questionnaire will assess the mothers' perceived feelings of autonomy, relatedness, and competence ("health care climate questionnaire"), and the other will assess the mother's internalization of the videotaped message (i.e., the degree to which mothers understood, agreed with, and perceived the oral health message as helpful and useful to them ["internalization questionnaire"]).
- SDT proposes that, if the participating woman has internalized the message, the changes should be evident within a short period of time.⁷ Thus, participating women from both groups will be asked to complete post-intervention questionnaires at *one-month follow-up* after viewing the videotaped messages at visits 1, 2 and 3 designed to assess mothers' changes in self-reported knowledge and subsequent oral health behavior towards their child's oral health. According to the informed consent approved by the UI IRB, "You (study participant) may feel uncomfortable in answering certain questions and you can choose to decline any aspect of the study at any time. You and your child may discontinue participating at any time without any negative consequences." Therefore, participants may choose not to complete the one-month follow-up questionnaires.

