9.2 SAMPLE SIZE DETERMINATION

Based on a sample size of 317, we should be able to entertain up to 31 covariates in a multiple regression model without jeopardizing model validity through overfitting (we note that this far exceeds the number of covariates targeted in this application, even allowing for reasonable examination of first-order interactions); this number would be smaller for logistic modeling, depending upon the distribution of the outcome variable. Finally, we note that modeling of outcomes such as clinical status and behavioral change can include covariates such as knowledge, behavioral intent, autonomy, competence, and relatedness. Such models incorporate the key aspects of the SDT intervention, can assist in the evaluation of the impact of SDT, and can offer validation of its application. The rich data set will permit formal evaluation of the validity of the theoretical basis of the proposed intervention, e.g., by evaluation of timing of behavioral change and whether it persists as prescribed by SDT, by assessing the relationships between outcomes and ratings of autonomy, competence and relatedness, and more systematically by use of mediation models.⁵⁸⁻⁶² While every effort will be made to maximize retention as outlined below, missing data issues will be addressed via multiple imputation^{63,64} the importance and utility of this approach have been substantiated for intervention trials targeting early childhood caries.⁶⁵ We will follow the general recommendations of Rubin^{66,67} and emulate the more specific aspects of execution of the caries-oriented analysis applied to these reported caries intervention trial data.⁶⁵ The possibility of selective dropout between the two groups will be fully explored, as will characteristics associated with dropout; sensitivity analyses will be conducted to explore the potential impact on results.

Power and Sample Size Considerations: Estimation of Detectable Effect Sizes

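### The primary caries model adjusts for mothers' knowledge and behavior without limiting them to pre-video Visit 1 values, so its intervention term may not be the intention-to-treat effect

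*Protocol*

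**What the plan says.** The primary objective (Protocol 1.1 and section 3) is the effect of the randomized intervention on the child's oral health. Section 9.4.2 states "Data will be analyzed on an intention-to-treat basis" and describes a longitudinal count model fitted by GEE. On covariates it says "The model will include age, gender, location (urban/rural), race, intervention, and mothers' knowledge and behavior", and adds that "mothers' intervention and behavior/knowledge are covariates of interest". No measurement time is attached to knowledge or behavior. If the data cannot carry all the covariates, "we will use bivariate analyses to inform a more parsimonious final model".

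The same two variables have other roles in the protocol:

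- Objective 2a tests whether the intervention acts on the child's oral health "through its mediating effects on mothers' changes in self-reported knowledge". Objective 2b does the same for changes in behaviors concerning the child.
- Section 9.4.3 lists changes in maternal knowledge and behavior as secondary outcomes, plans a separate mediation analysis, and carries the primary model's covariates into the secondary models.
- Section 9.2 says that "modeling of outcomes such as clinical status and behavioral change can include covariates such as knowledge, behavioral intent, autonomy, competence, and relatedness".

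The schedule in 1.3 has mothers complete knowledge and behavior questionnaires at Visit 1 and again at follow-ups after randomization.

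**The concern.** Randomization protects a comparison that is unadjusted or adjusted only for variables fixed before treatment. A variable that the treatment is meant to change does not qualify. Conditioning on it removes from the intervention coefficient whatever part of the effect passes through it. It also opens a route for bias, because unmeasured causes shared by maternal behavior and child caries are not balanced within levels of a post-randomization variable.

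Section 2.2 presents gains in maternal knowledge and behavior as what produces the children's benefit. The better that theory holds, the more of the true effect a mediator-adjusted model would remove. A trial whose intervention worked as designed could report a primary rate ratio close to 1. Readers would take that ratio as the intention-to-treat effect, because 9.4.2 labels it so.

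**Working it through.** **1. Which measurement does the text mean?** Both readings are possible.

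- *For Visit 1:* both mother questionnaires are scheduled there, and 6.1.2 says the pre-video questionnaires cover the mother's own diet, hygiene and dental visits.
- *For later values:* section 9.2 allows models of clinical status to include autonomy, competence and relatedness. Section 6.1.2 has these rated "Immediately after viewing the videotaped oral health messages at visits 1, 2 and 3". The item "Mother behavior intent questionnaire" is marked in the schedule only at Visit 4. The behaviors in objective 2b are directed at the child and cannot be observed before birth.
- The label *pre-intervention* does not settle it. The questionnaires so named at Visits 2 and 3 come after randomization and after at least one scheduled video.

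Nothing in the protocol restricts the covariate to Visit 1.

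**2. The protocol's own sample size (9.2) reproduces.** Inputs: difference 1.1, SD 3.45, alpha 0.05 (taken as two-sided), power 80%.

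- Normal approximation: n = 2 × (1.960 + 0.842)² × (3.45/1.1)² = 154.4, so 155 per group. The t-test gives 155.4, so 156, as stated.
- Attrition: 317 × 0.79³ = 156.3 per group.
- For 1.7 with SD 4.35 at 156 per group, power is 93%, as stated.

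The planned power is therefore power for the total difference.

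**3. What is left if mediators are conditioned on.** Let m be the share of the effect that passes through the adjusted variables. On a linear scale, with the mediator measured without error, the remaining difference is Δ × (1 − m). The protocol gives no value for m, so a range is shown (two-sided t-test, 156 per group).

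| m | Remaining of 1.1 (SD 3.45) | Power | Remaining of 1.7 (SD 4.35) | Power |
|---|---|---|---|---|
| 0% | 1.100 | 80% | 1.700 | 93% |
| 25% | 0.825 | 56% | 1.275 | 73% |
| 50% | 0.550 | 29% | 0.850 | 41% |
| 75% | 0.275 | 11% | 0.425 | 14% |

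For the 1.1 difference, power falls to 50% at m of about 30%.

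**4. Does the same happen with a log-link count model?** Two simulations used 156 per group, three visits, over-dispersed counts and a Poisson log link with robust variance. Both used working independence instead of the planned AR(1), and both assumed that the intervention shifts the mediator by 0.5 SD.

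*Assumed total IRR 0.60, 1,000 runs:*

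| m | IRR (rejection rate), baseline value adjusted | IRR (rejection rate), post-randomization value adjusted |
|---|---|---|
| 0% | 0.60 (97%) | 0.60 (96%) |
| 50% | 0.60 (92%) | 0.77 (45%) |
| 100% | 0.60 (68%) | 0.99 (8%) |

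*Total effect tied to the 1.1 difference, m = 50%, 36-month SD about 3.45, 2,000 runs:*

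- Assumed control mean 3.0: total IRR = (3.0 − 1.1)/3.0 = 0.63. Adjusted IRR is 0.80, and power falls from 87% unadjusted to 38% adjusted.
- Assumed control mean 2.0: total IRR = (2.0 − 1.1)/2.0 = 0.45. Adjusted IRR is 0.66, and power falls from 91% to 52%.
- Adding an unmeasured cause of both mediator and caries (0.3 SD on the mediator, ∓0.4 on the log rate) moves the adjusted IRR to 0.84 or 0.75 at control mean 3.0, and to 0.71 or 0.63 at 2.0. The bias can go either way.

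**The case against.** The strongest reply is that the harm depends on timing that the protocol does not state, and that timing could be fixed in a statistical analysis plan not shown here. Section 9.4.2 lists the variables with age, gender, location and race as known correlates of caries, which reads like ordinary prognostic adjustment. It speaks of mothers' behavior, while the schedule has a separate child behavior questionnaire, so the point about behaviors before birth is not decisive. Section 9.2 is permissive, seems to describe theory-validation models, and names constructs absent from the 9.4.2 list. Section 2.2 also suggests that intention is asked after the videos, so the Visit 4 entry is weak evidence about 9.4.2.

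Much of this stands: a Visit 1 reading is reasonable. It does not remove the problem, because 9.4.2 already commits these variables to the primary model and calls them covariates of interest beside the intervention. An analysis plan using post-randomization values would comply with that text.

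An unadjusted comparison does survive, in the by-group descriptive counts and in the total-effect step of the mediation analysis. Neither is designated as the primary result.

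The magnitudes are also fairly challenged. They rest on assumed shares, and imperfect questionnaires would remove less. With 50% mediated and an assumed reliability of 0.6, about 1.1 − 0.6 × 0.55 = 0.77 remains, with power of about 50% instead of 29%. The direction is unchanged.

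**Conclusion.** The concern holds and should be fixed before analysis. The protocol fixes its one primary model so that a compliant analysis can condition on the declared mediators and report the result as intention-to-treat. Whether that happens depends on which measurement is used, and the text leaves this open. The fallback to a smaller model does not help, because it lets the data decide whether the coefficient is adjusted for mediators.

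Confidence is high that the time limit is missing and that mediator adjustment changes what is estimated. The size is illustrative. It rests on an assumed mediated share, control mean, mediator shift and confounder strength, and on a t-test and an independence working model in place of the planned GEE with AR(1) and multiple imputation. With baseline adjustment in the simulation, the intervention ratio stayed at the assumed 0.60 whatever the mediated share.

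**What to change.** In 9.4.2, do one of two things:

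- remove mothers' knowledge and behavior from the primary model; or
- state that they enter only as values measured at Visit 1, before the first video.

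Name the visit explicitly, since the word *pre-intervention* also covers Visits 2 and 3. Reserve all post-randomization knowledge and behavior values for the mediation analyses of objectives 2a and 2b.

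In 9.4.3, apply the same limit, so that no post-randomization knowledge or behavior value, including the outcome's own, is a covariate in a secondary efficacy model. Where the Visit 1 value is already part of the outcome (pre and post knowledge counts, improvement in behavior), say which role it takes.

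The cost is one wording change in each of the two sections. No new data, visits or participants are needed, because the Visit 1 questionnaires are already scheduled.

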6.3 MEASURES TO MINIMIZE BIAS: RANDOMIZATION AND BLINDING

A block-level randomization scheme with a 1:1 allocation ratio will be used to determine interventions for individuals. Random block sizes of 2, 4, and 6 will be used to create the randomization scheme. Randomization will be stratified on primary language and site to ensure balance between the intervention groups. Subjects, clinical examiners, and data analyst will be blinded with respect to treatment allocation; care will be taken to maintain allocation concealment. However, the study CTRA and RAs will not be blinded so that they can deliver the assigned intervention as a supervised exposure to prevent contamination, as a further measure to ensure rigor and transparency. In addition, the study statisticians will be not be blinded in order to manage the dataset, check randomization, check the REDCapTM, etc.

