9.4.3 ANALYSIS OF THE SECONDARY ENDPOINT(S)

Secondary efficacy

Secondary outcomes of interest include changes in knowledge and oral health behaviors of mothers, as well as plaque and microbial outcomes in children. Knowledge outcomes will be measured pre and post intervention via the score on the knowledge assessment. These measures will be considered as counts. GEE modeling will be used with Poisson or negative binomial distributions considered. Results will be presented as incidence rate ratios and 95% confidence intervals.

Maternal change in behavior will be assessed via a set of behavioral questions asked at multiple time points. Each individual question will be dichotomized into improved vs. did not improve based on the answers given pre and post intervention. When analyzing single time points, logistic modeling will be used. To evaluate behavioral changes over time, GEE models with a logit link function will be used. Results will be presented as odds ratios and 95% confidence intervals.

Visible plaque will be analyzed as the number of maxillary and mandibular incisors and molars with plaque at each visit. Analysis of plaque outcomes will focus on Poisson and/or negative binomial modeling, possibly with variance inflation and zero inflation accommodation, as appropriate. To account for repeated longitudinal measurements, GEE will be used to model these counts. Results will be presented as incidence rate ratios and 95% confidence intervals.

Levels of salivary MS will be reported as numbers of bacteria from each visit. Log transformation will be considered if data is skewed, and GEE models assuming a normal distribution with an identity link will be used when analyzing multiple time points. Results will be presented as adjusted least squares means estimates and 95% confidence intervals.

The same covariates as the primary endpoint will be used for both bivariate and multivariable modeling, subject to the constraint of 10 observations/events for every covariate included. Missing data may be addressed via multiple imputation. An AR(1) correlation structure will be assumed for all longitudinal models. QIC will be used for all model/covariate selection involving GEEs; AIC will be used for models calculated for single time points. Mediation analyses will proceed via Baron and Kenny's⁷⁴ steps for mediation analysis and significance will be calculated via Sobel tests.

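### Randomization is stratified on primary language and site, but the covariate list fixed in 9.4.2 and reused in 9.4.3 contains neither: a small mismatch between design and analysis

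*Protocol*

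**What the plan says.** Protocol 9.4.1 states: "Randomization will be stratified on primary language and site to ensure balance between the intervention groups". The same scheme is given in 6.3 and in the detailed description of the intervention under 6.1.2. Sections 6.1.2 and 9.4.1 put the number of possible sites at 12, so there are up to 24 language-by-site strata.

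For the primary endpoint, 9.4.2 gives an explicit list: "The model will include age, gender, location (urban/rural), race, intervention, and mothers' knowledge and behavior". For the secondary endpoints, 9.4.3 says: "The same covariates as the primary endpoint will be used for both bivariate and multivariable modeling". A limit is attached to that reuse, which is made "subject to the constraint of 10 observations/events for every covariate included".

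Both sections allow the list to shrink. In 9.4.2, "if the number of covariates is limited by the sample size or infrequent observations of caries, we will use bivariate analyses" to reach a smaller final model. In 9.4.3, "QIC will be used for all model/covariate selection involving GEEs; AIC will be used for models calculated for single time points". Nowhere does the protocol describe a stratified test, a site effect or any other way of carrying the strata into the analysis.

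**The concern.** When randomization is stratified, the arms are balanced on the strata by construction, so the true variance of the treatment comparison is smaller than under simple randomization. A model without the strata does not know this. If the strata predict the outcome, its standard error is a little too large and part of what stratification bought is lost.

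Location has two levels against 12 sites, and race is not language, so the listed covariates recover only part of the strata information. Even that part is not secure, because location and race can themselves be removed by bivariate screening or by QIC/AIC selection.

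This is not merely a detail left to the SAP. The protocol fixes a list. A SAP that followed it would leave out both design factors, and a SAP that added them would depart from the protocol. At stake is a standard error consistent with the design, and a small amount of efficiency.

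**Working it through.** **1. The plan's own figure.** Inputs from Protocol 9.2: difference 1.1, SD 3.45, type I error 0.05 (taken as two-sided), power 80%. The normal approximation gives 155 per group and the t-based calculation gives 156, as stated. Retention: 317 × 0.79³ = 156.3, which agrees with the 156 expected per group. Normal-approximation power at 156 is 80.4%.

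**2. How much too large is the standard error?** The documents give no R2 for language and site, so a range is assumed, with half of it already captured by location and race.

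- Share of the remaining variance due to the strata: r = (R2/2) / (1 − R2/2).
- Stratified blocks balance the women randomized. After random dropout only the fraction 156/317 = 0.492 of that balance carries over to completers.
- SE excess = 1/√(1 − r × 156/317) − 1.

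| Assumed strata R2 | r | r × 156/317 | SE too large by |
|---|---|---|---|
| 0 | 0 | 0 | 0% |
| 0.05 | 0.0256 | 0.0126 | 0.64% |
| 0.10 | 0.0526 | 0.0259 | 1.32% |
| 0.20 | 0.1111 | 0.0547 | 2.85% |

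**3. A generous bound on the power gain.** Take a linear model at 156 per group, give location and race no credit, and ignore the dilution by dropout. With the strata in the model, the SD becomes 3.45 × √(1 − R2). With the strata left out, the test uses the unreduced SD although the true variance is the reduced one.

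| R2 | Power, strata in | Power, strata out | Actual two-sided alpha, strata out |
|---|---|---|---|
| 0.02 | 81.2% | 80.6% | 0.048 |
| 0.05 | 82.4% | 81.0% | 0.044 |
| 0.10 | 84.3% | 81.6% | 0.039 |
| 0.15 | 86.3% | 82.3% | 0.034 |

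The gain is about 0.5 to 4.0 points. Omission makes the test conservative, and power stays above 80% throughout.

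**4. A count-model check.** This was a simulation of 4,000 trials per setting: 634 women in 24 strata, permuted blocks of 2, 4 and 6, random retention of 156/317, and negative binomial counts at 36 months (means 2.5 and 1.4, SD about 3.4). Each trial was analysed by Poisson regression with a Mancl-DeRouen corrected robust variance. The comparator already contained location and race. The alternative contained race, language and pooled site groups.

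| R2 | Power, location and race | Power, language and pooled sites | Change |
|---|---|---|---|
| 0 | 83.4% | 82.6% | −0.8 |
| 0.05 | 85.7% | 85.5% | −0.2 |
| 0.10 | 85.2% | 85.8% | +0.6 |
| 0.20 | 87.3% | 89.1% | +1.8 |

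Monte Carlo error on each power is about 0.6 points, with both models fitted to the same trials. The language share, site sizes, caries means and the race-language link are assumptions, so only the differences are informative.

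**5. Cost in model terms.** One language term plus 11 site terms makes 12. At 10 observations or events per covariate, that needs 12 × 10 = 120. If pooling leaves about five terms in all, it needs 5 × 10 = 50.

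**The case against.** The strongest case against is that the benefit has no known sign. Once location and race are in the model, the count-model check moves power by −0.8 to +1.8 points, and the gain exceeds 1 point only at R2 = 0.20. The larger gains in the linear calculation come from giving the proxies no credit and ignoring dropout. The check is also not the planned analysis: it uses one time point, completers and a Poisson model, whereas 9.4.2 plans a longitudinal GEE with AR(1) correlation and multiple imputation. All of this stands, and it rules out presenting the change as a power gain.

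Three limits on any remedy also stand.

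- Uncorrected robust errors gave type I error of 5.1% to 5.8% in the simulation with location and race alone. Small-sample variance correction is therefore a separate matter, not a consequence of omitting the strata.
- The protocol does not say whether urban/rural location is defined by clinic or by residence, so there is no basis for asking that location be dropped.
- Pooling sites by numbers of children examined would make the groups depend on retention after randomization. Numbers randomized avoid this.

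The objection does not remove the mismatch itself. The list is explicit, it omits both factors, and nothing elsewhere in the protocol makes up for it.

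**Conclusion.** The point holds at low severity. The stated models do not include the factors by which the trial randomizes, and the proxies in the list cover them only in part. The reported standard error is too large by about 0.6% to 2.9% for an assumed strata R2 of 0.05 to 0.20, half captured by location and race, under the planned attrition. If the strata do not predict caries, nothing is lost by omitting them, and including them costs up to about 1 point of power.

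A reader might infer that the omission biases the treatment effect, inflates type I error or leaves the trial underpowered. The documents support none of these. Allocation is 1:1 within strata, the error runs in the conservative direction, and the sample size of 156 per group reproduces without any credit for the strata.

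The size rests on assumed R2 values and on random dropout. The textual mismatch rests on no assumption. Whether mothers' knowledge and behavior belong in the same model is a separate question, on which this point takes no position.

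**What to change.** Add to Protocol 9.4.2 and 9.4.3:

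> Primary language and WIC site, the randomization factors, are included in the between-group models and retained irrespective of bivariate screening and QIC/AIC selection. Small sites are pooled by a rule fixed before outcome data are examined by arm, based on numbers randomized with arms combined.

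The timing is tied to outcome data by arm, not to unblinding, because 6.3 says "the study statisticians will be not be blinded in order to manage the dataset". The pooling threshold and the coding of any sites added under 5.5 can be left to the SAP.

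The cost is wording in two sections, with no new data. The model spends up to 12 degrees of freedom before pooling. Section 9.2 allows up to 31 covariates in a multiple regression, but adds that "this number would be smaller for logistic modeling, depending upon the distribution of the outcome variable". Where the limit of 10 observations or events per covariate in 9.4.3 binds, the retained strata may displace other planned covariates.
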